2.4.2.2.2 Analysis of PNALD

PNALD will be summarized at each visit as well as at the post-baseline maximal value (maximal being 'yes' to developing PNALD at any timepoint) by treatment group using frequencies and percentages.

If there are more than 5 cases of PNALD per arm, then time to develop PNALD will be analyzed using survival analysis approach (cumulative incidence), and the mean, standard error, Q1, median, Q3, minimum, and maximum for each treatment group will be displayed, where calculable. A cumulative incidence plot will also be produced. If there are less than 5 cases of PNALD in each treatment arm, then time to developing PNALD will be summarized descriptively by treatment group for all patients developing PNALD using n, mean, standard deviation, minimum, Q1, median, Q3, and maximum. If no events occur, then time to PNALD will not be calculated.

The incidence rate of PNALD will be computed and displayed per treatment group. The proportion of PNALD will be summarized per treatment group as the number of patients who develop PNALD divided by the corresponding total number of patients in each group.

A spaghetti plot consisting of direct bilirubin values over time will be produced with one line representing each patient, and different types of lines or symbols (e.g. solid and dashed) representing each treatment group. A bolded line will be added at y=2 to represent the bound for PNALD.

2.4.2.3 Hepatic Integrity

Hepatic integrity (ALP, AST, ALT, GGT, total and direct bilirubin) will be evaluated by presenting descriptive summary statistics (number of patients, mean, standard deviation, Q1, median, Q3, minimum, and maximum) at different measurement time points from baseline to end of study treatment during the study period in each of the 2 treatment groups (Clinolipid vs Intralipid). Change from baseline will also be summarized.

Each hepatic integrity parameter will also be summarized in shift tables comparing end of study treatment and post-baseline maximal values during the study intervention with those at baseline. Shift categories will include normal and abnormal (>1 to 3 and >3-fold the upper limit of normal range). If a patient is below the normal range, they will be included as 'normal' for this analysis.

The delay (days) between baseline and post-baseline maximal value in each of the 2 treatment groups (Clinolipid vs Intralipid) will also be summarized using n, mean, standard deviation, minimum, Q1, median, Q3, and maximum. Days between baseline and post-baseline maximal value will be calculated by the following:

(Date of Maximal Lab Value – Date of Baseline) + 1

If there are two instances of the same maximal value post-baseline, then the first instance of the maximal value will be used as the date of maximal lab value.

In addition, assessment for drug-induced liver injury (DILI) will be conducted according to Hy's Law and eDISH criteria,^{1,2}. This will be assessed using two scatterplots in the log log scale between the peak aminotransferase (AT) levels (x upper limit normal (ULN)) and peak total bilirubin (TB) level (xULN) per patient. The two ATs that will be used are AST and ALT. Boundary lines will be put in at x=1 and y=1 signaling the 'box' for the normal range as well as y=3 and x=2 to signify the boundaries for Hy's Law (when peak AT > 3xULN and peak TB >2xULN). To calculate peak AT/TB x ULN,

Maximum AT/TB Upper Limit of Normal

Different symbols will be used per treatment group.

If any patients appear in the Hy's law range, then the time course of all liver tests (ALT, AST, ALP, and TB) will be shown per patient (one graph per patient who meets Hy's law criteria). The y axis will be the test values x ULN on the log scale, and the x axis will be the time from start of treatment.

2.4.2.4 Plasma Phytosterols, Cholesterol, and Squalene Levels

Plasma phytosterols (stigmasterol, campesterol, and sitosterol), cholesterol, and squalene levels will be summarized using descriptive statistics (mean, standard deviation, Q1, median, Q3, minimum, and maximum) at baseline and the end of study treatment, as well as post-baseline maximal value during the study and the delay (days) between study baseline and post-baseline maximal value in each of the 2 treatment groups (Clinolipid vs Intralipid). In addition, the correlation between plasma phytosterol levels and direct bilirubin values will be assessed by computing a Pearson's correlation coefficient or a Spearman correlation coefficient depending on whether the normality assumption is fulfilled. Normality will be assessed visually with a QQ plot. Values will be paired by patient and visit. A scatterplot of plasma phytosterol and direct bilirubin values will also be produced with different symbols for each of the two different treatment groups.

2.4.3 Adequacy of Nutritional Interventions

Prescribed (ordered) and actual (administered) nutritional intake (fluid, energy, protein, carbohydrates, and lipids) from parenteral, enteral nutrition, and IV fluids will be collected and recorded daily. They will be summarized descriptively on a daily basis during the first 2 weeks of treatment and on a 15-day basis afterwards up to end of study treatment for each of the treatment groups. Summaries of overall nutritional intake will also be done. Box plots will also be produced by day and treatment group.

2.4.3.1 Parenteral Nutritional Intake

Data from parental nutrition will be calculated as follows:

Fluid intake ordered (mL/kg/24 hours):

24 * Total volume ordered(mL) PN dosing weight (kg) Total PN Infusion Duration (hours)

Fluid intake administered (mL/kg/24 hours):

24 * Total volume administered(mL) PN dosing weight (kg) Total PN Infusion Duration (hours)

Energy intake ordered (kCal/kg/24 hours):

Total calories (kCal) should first be calculated as³:

Protein intake (g/kg) *PN dosing Weight (kg) * 4 + Lipid intake (g/kg) * lipid dosing weight (kg) * 10 + $\frac{Carbohydrate intake (g/dL)}{100}$ * Fluid intake ordered (mL/kg) * PN dosing Weight(kg)*3.4 Then energy intake can be calculated as:

> 24 * Total calories (kCal) PN dosing Weight (kg) Total PN Infusion Duration (hours)

Energy intake administered (kCal/kg/24 hours):

Total Volume Administered
Total Volume Ordered* Energy Intake Ordered

Protein intake ordered (g/kg/24 hours):

24 * Protein intake (g/kg) Total PN Infusion Duration (hours)

Protein intake administered (g/kg/24 hours):

Total Volume AdministeredTotal Volume Ordered* Protein Intake Ordered

Carbohydrate intake ordered (g/kg/24 hours):

Dextrose intake (g/dL) * Total volume ordered (mL)24 *100 * PN dosing weight (kg)Total PN Infusion Duration (hours)

Carbohydrate intake administered (g/kg/24 hours):

Total Volume AdministeredTotal Volume Ordered* Carbohydrate Intake Ordered

Lipid intake ordered (g/kg/24 hours):

 $\frac{24 * \frac{0.2(\frac{g}{mL}) * Total \ lipid \ volume \ ordered \ (mL)}{Lipid \ dosing \ weight \ (kg)}}{Total \ Lipid \ Infusion \ Duration \ (hours)}$

Lipid intake administered (g/kg/24 hours):

$$\frac{24 * \frac{0.2 \left(\frac{g}{mL}\right) * \text{ Total lipid volume administered (mL)}}{\text{Lipid dosing weight (kg)}}}{\text{Total Lipid Infusion Duration (hours)}}$$

If lipid dosing weight is missing, PN dosing weight will be used instead. If both are missing, the recorded weight on the closest, prior non-missing day will be used.

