5.2 Treatments Administered

Study treatment will be administered intravenously in the hospital setting from 7 up to 90 days using either a syringe pump or an infusion pump as appropriate for the daily volume of infusate. The flow rate will be prescribed by the Investigator to provide the daily dosage over 20 to 24 hours (maximum lipid infusion rate should not exceed 0.15 g/kg/hour).

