6.8.5 Calculating Linoleic Acid (LA) Intake from Intravenous Lipid Emulsion (ILE)

Clinolipid contains approximately 18.6% LA while Intralipid contains approximately 54.7% LA. Since both are 20% ILE (20 g/dL, 0.2 g/mL, 2 kcal/ml), the content of LA is approximately 0.11 g/mL for Intralipid (1.1 kcal/ml from LA) and 0.04 g/mL for Clinolipid (0.4 kcal/ml from LA) (Table 6).

Content	20% Intralipid	20% Clinolipid
Lipid, g/ml	0.2	0.2
Energy, kcal/ml	2	2
Linoleic acid, g/ml	0.11	0.04
Linoleic acid, kcal/ml	1.1	0.4

Table 6. Intralipid and Clinolipid Linoleic Acid Content

Sample Calculation:

If a 2 kg patient receives 16 mL of Intralipid per day, the patient receives 8 ml/kg/day of Intralipid. It corresponds to 1.6 g/kg/day of lipid and 0.88 g/kg/day of LA. The energy part of LA is 8.8 kcal/kg/day. If the total energy intake is 100 kcal/kg/day, it means that 8.8% of the energy intake comes from LA.

If a 2 kg patient receives 16 mL of Clinolipid per day, the patient receives 8 ml/kg/day of Clinolipid. It corresponds to 1.6 g/kg/day of lipid and 0.32 g/kg/day of LA. The energy part of LA is 3.2 kcal/kg/day. If the total energy intake is 100 kcal/kg/day, it means that 3.2% of the energy intake comes from LA.

The LA intake that normally prevents EFAD is 1-4% of total energy intake. The unblinded pharmacist determines if the patient has adequate LA intake for prevention of EFAD. The pharmacist communicates to the patient's nutrition clinician according to the protocol (see Sections 6.8.2, 6.8.3 and 6.8.4.).

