0.019 g/mL	0.069 g/mL	0.038 g/mL
0.024 g/mL	0.083 g/mL	0.044 g/mL
0.021 g/mL	0.075 g/mL	0.041 g/mL
0.052 g/mL	0.16 g/mL	0.068 g/mL
0 g/mL	0.028 g/mL	0 g/mL
	Protein 0.012 g/mL 0.019 g/mL 0.033 g/mL 0.014 g/mL 0.019 g/mL 0.019 g/mL 0.019 g/mL 0.019 g/mL 0.019 g/mL 0.021 g/mL 0.052 g/mL 0 g/mL	Protein Carbohydrate 0.012 g/mL 0.074 g/mL 0.019 g/mL 0.074 g/mL 0.033 g/mL 0.122 g/mL 0.014 g/mL 0.076 g/mL 0.019 g/mL 0.069 g/mL 0.019 g/mL 0.069 g/mL 0.019 g/mL 0.069 g/mL 0.019 g/mL 0.069 g/mL 0.021 g/mL 0.075 g/mL 0.052 g/mL 0.16 g/mL 0 g/mL 0.028 g/mL

Table 2. Conversion Factors

Breastmilk or formula (with additive or fortifier): The amount of additive/fortifier received will need to be calculated and used in the formulas. It can be calculated as:

 $\frac{Total \ Quantity \ Ordered \ (mL)}{Total \ Volume \ Ordered \ In(mL)} * Total \ Volume \ Received \ (mL)$

Fluid intake ordered (mL/kg/24 hours):

 $\frac{Total \ volume \ ordered \ (mL) + Total \ volume \ ordered \ of \ additive \ (mL)}{Weight \ on \ that \ day \ (kg)}$

If total volume ordered is recorded in ml/3 hours, then the amount should be multiplied by 8 to find the total volume ordered in mL per 24 hours. If total volume ordered is recorded in ml/2 hours, then the amount should be multiplied by 12.

Fluid intake administered (mL/kg/24 hours):

 $\frac{Total \ volume \ received \ (mL) + Total \ volume \ of \ additive/fortifier \ (mL)}{Weight \ on \ that \ day \ (kg)}$

Energy intake ordered (kCal/kg/24 hours):

Modified kcal in formulation per mL * Total Volume Ordered (mL) Weight on that day (kg)

Energy intake administered (kCal/kg/24 hours):

Modified kcal in formulation per mL * Total Volume Received (mL) Weight on that day (kg)

Protein intake ordered (g/kg/24 hours):

 $Protein intake ordered from 2.4.3.2 + \frac{Total Volume Ordered of Additive(mL, packet, or g) * Protein Conversion from Table 3}{Weight on that day (kg)}$

Protein intake administered (g/kg/24 hours):

Protein intake administered from 2.4.3.2 + $\frac{Total Volume Received of Additive(mL, packet, or g) * Protein Conversion from Table 3}{Weight on that day (kg)}$

Carbohydrate intake ordered (g/kg/24 hours):

Carb intake ordered from 2.4.3.2 + $\frac{Total Volume Ordered of Additive(mL, packet, or g) * Carb Conversion from Table 3}{Weight on that day (kg)}$

Carbohydrate intake administered (g/kg/24 hours):

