2.4.3.3 Intravenous Fluid Nutritional Intake

Only fluid intake administered, energy intake administered, and carbohydrate intake administered will be calculated for intravenous fluid intake as protein and lipid intake are 0 g/mL. These will be calculated as follows:

Fluid intake administered (mL/kg/24 hours):

$$\frac{24 * \frac{Total \ volume \ administered(mL)}{Weight \ on \ that \ day(kg)}}{Total \ Infusion \ Duration \ (hours)}$$

Energy intake administered (kcal/kg/24 hours):

$$\frac{24 * 3.4 \left(\frac{kcal}{g}\right) * \frac{Percentage \ Dextrose * \frac{Total \ volume \ administered \ (mL)}{100}}{Weight \ on \ that \ day \ (kg)}}{Total \ Infusion \ Duration \ (hours)}$$

Carbohydrate intake administered (g/kg/24 hours):

24 * Percentage Dextrose * Weight	Total volume administered (mL)	
	100	
	Weight	t on that day (kg)
То	tal Infusio	n Duration (hours)

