2.4.3.4 Overall Nutritional Intake

Overall nutritional intake (ordered and administered) will be calculated per patient per day for fluid intake and energy intake by summing the following:

PN Intake + EN intake + IV Fluid intake

The percentage of PN and EN for fluid and energy intake will be calculated as follows:

Percentage of PN administered:

 $\frac{Total \ PN \ intake \ administered}{Total \ overall \ intake \ administered} x100\%$

Percentage of EN administered:

 $\frac{Total \ EN \ intake \ administered}{Total \ overall \ intake \ administered} x100\%$

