2.5.2.6 Derivation of Treatment Exposure

The following will be calculated to summarize treatment exposure:

Infusion duration (in hours/day):

End datetime of administration - Start datetime of administration

If multiple infusions were given each day, then the above will be done for each administration and summed together.

Administered Daily Infusion Rate (mL/kg/day):

Total Volume Administered on Day X (mL) Lipid dosing weight on Day X (kg)

Administered Daily Dose (g/kg/day):

 $\frac{Total Volume Administered on Day X (mL)}{Lipid dosing weight on Day X (kg)} * 0.2$

Administered Infusion Rate (g/kg/h):

Administered Daily Dose (g/kg/day) Infusion Duration (hr/day)

Total Study Treatment Days (days):

(End Date of Study Treatment - Start Date of Study Treatment) + 1

Total Pre-Study Treatment Days (days): a count of the number of days that prerandomization lipids were reported. If a patient had more than one infusion per day, then the sum of all infusions over that day should be used in the calculations above. For example, if there are two infusions of 200 mL each over 4 hours a piece, the total volume administered should be 400 mL and the total treatment duration should be 8 hours.

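### SAP parenteral and IV intake formulas give 24-hour rates, not daily amounts, and then add them to unscaled enteral intake

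*SAP*

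**What the plan says.** SAP 2.4.3 treats nutritional adequacy as ordered and actually administered intake, recorded daily. Its subsections then use different definitions.

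- **Parenteral (SAP 2.4.3.1).** Administered fluid is "24 * Total volume administered(mL) PN dosing weight (kg) Total PN Infusion Duration (hours", read with its fraction bars as 24 × (volume ÷ weight) ÷ hours. Ordered fluid, ordered and administered lipid, and ordered energy, protein and carbohydrate carry the same factor. Administered energy, protein and carbohydrate inherit it, being the ordered value times a volume ratio.
- **IV fluids (SAP 2.4.3.3).** "Only fluid intake administered, energy intake administered, and carbohydrate intake administered will be calculated for intravenous fluid intake"; all three have the 24/duration factor.
- **Enteral (SAP 2.4.3.2).** Intake is volume (times a conversion where needed) ÷ weight, with same-day records summed and no duration term. For feeds with an additive, the text says "The amount of additive/fortifier received will need to be calculated and used in the formulas".
- **Overall (SAP 2.4.3.4).** Fluid and energy are totalled as "PN Intake + EN intake + IV Fluid intake", and the PN and EN percentages come from that total.
- **Exposure (SAP 2.5.2.6).** The administered daily lipid dose is "Total Volume Administered on Day X (mL) Lipid dosing weight on Day X (kg") × 0.2, with no duration term.
- **Protocol 6.8.5.** For a 2 kg patient given 16 mL of Intralipid in a day: "It corresponds to 1.6 g/kg/day of lipid and 0.88 g/kg/day of LA".
- **Protocol 5.2.** The infusion is run "to provide the daily dosage over 20 to 24 hours".

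**The concern.** Multiplying an amount by 24 and dividing by infusion hours answers what would have been given had the infusion run all day at that rate. The endpoint asks what was ordered and what was given. The two agree only at 24 hours, and the protocol allows shorter infusions.

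Three things follow when the duration is not 24 hours. The parenteral and IV tables misstate absolute intake. The parenteral intake table (14.3.6.4.1) and the exposure table (14.3.10) show different lipid doses for the same patient-day. The overall totals and PN/EN shares mix scaled with unscaled terms. The study is descriptive, so these absolute values are themselves the result for this secondary endpoint.

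Two definitions are also open. The SAP does not say whether duration means planned or actual hours. The calorie formula uses an ordered fluid term without saying whether it is raw or already scaled.

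**Working it through.** **Inputs.** Lipid content 0.2 g/mL (SAP 2.4.3.1, 2.5.2.6); 16 mL in 2 kg (Protocol 6.8.5); lipid duration T of 20–24 h (Protocol 5.2). PN hours, IV hours and the PN/EN split are not in the documents and are assumed where marked.

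**1. The protocol's own figure.** The unscaled formula of SAP 2.5.2.6 gives 0.2 × 16 ÷ 2 = 1.6 g/kg/day, matching Protocol 6.8.5. The formula of SAP 2.4.3.1 gives 24 × 1.6 ÷ T, which is 1.6 only at T = 24.

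**2. Lipid across the allowed window.** Error factor = 24/T.

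| T (h) | 24/T | 1.6 g/kg reported as | 3 g/kg reported as |
|---|---|---|---|
| 24 | 1.00 | 1.60 | 3.00 |
| 22 | 1.09 | 1.75 | 3.27 |
| 20 | 1.20 | 1.92 | 3.60 |

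SAP 2.5.2.6 reports 1.6 and 3.0 on every row. Its own illustration of 400 mL over 8 hours differs between the two sections by 24/8 = 3 at any weight.

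**3. Interrupted infusion (assumed: 3 g/kg ordered over 24 h, stopped at 12 h with 1.5 given).**
- Actual hours used for both: ordered 24 × 3 ÷ 12 = 6.0; administered 24 × 1.5 ÷ 12 = 3.0. The ratio of 50% is right, but both absolute values are doubled.
- Planned hours for ordered, actual for administered: 24 × 3 ÷ 24 = 3.0 and 24 × 1.5 ÷ 12 = 3.0. The shortfall disappears.

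The second pattern affects lipid and fluid only. Administered energy, protein and carbohydrate use the volume ratio and keep the shortfall.

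**4. Overall energy (assumed: 60 kcal/kg PN, 40 kcal/kg enteral; true total 100, PN share 60%).**
- T = 24: 60 + 40 = 100; 60%.
- T = 22: 60 × 24/22 = 65.45; total 105.5; share 65.45/105.45 = 62.1%.
- T = 20: 60 × 24/20 = 72; total 112; share 72/112 = 64.3%.

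**5. IV fluids (assumed 10 mL/kg given).** Reported as 10 at 24 h, 10 × 24/12 = 20 at 12 h, and 10 × 24/4 = 60 at 4 h.

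**6. Calorie formula.** If its ordered fluid term is the scaled variable, the carbohydrate part is scaled twice: (24/20)² = 1.44 at 20 h.

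**7. Additive lipid, a separate point.** In SAP 2.4.3.2 the administered protein and carbohydrate formulas use the additive volume received; the administered lipid formula uses the volume ordered. With an assumed 2 kg patient, 10 mL of additive ordered, half received, and 0.116 g/mL from SAP Table 3, the formula gives 10 × 0.116 ÷ 2 = 0.58 g/kg/day; the amount received is 5 × 0.116 ÷ 2 = 0.29.

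**The case against.** The strongest reply is that the affected lines are labelled per 24 hours, so a normalised rate may be intended and the formulas compute what they say. That does not rescue them. The enteral formulas carry the same label with no duration factor, and SAP 2.4.3 promises actual administered intake. The enteral ×8 and ×12 rules only convert orders written per 3 or 2 hours to daily totals.

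Other points stand as limits:
- There is no error on any day with a 24-hour infusion. Some sites will use that, and the mix of durations is unknown.
- The only range the documents support is 0% to 20% for lipid. The other illustrations rest on assumed hours and splits. At 20 hours the PN share moves less when PN dominates: 73.7% against 70% for a 70/30 split (84/114), and 82.8% against 80% for 80/20 (96/116).
- Protocol 6.8.5 states no infusion hours and serves the pharmacist's linoleic acid check. It shows the usual meaning of g/kg/day and is not an analysis rule.
- The exposure table gives an unscaled dose for study lipid, so a reader could detect that discrepancy. PN fluid, energy, protein and carbohydrate, IV intake and overall intake have no unscaled counterpart.
- The additive wording is probably a typographical slip, and it affects enteral lipid only.

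**Conclusion.** The concern holds. As written, SAP 2.4.3.1 and 2.4.3.3 overstate the daily amount by 24/T whenever the infusion runs for less than 24 hours: up to 20% for lipid within the protocol's window, and more for interrupted PN or short IV infusions if those occur. The direct conflict with SAP 2.5.2.6 concerns study lipid; the mixing with enteral values concerns fluid and energy, the only quantities summed in 2.4.3.4.

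Administered/ordered ratios survive if one duration is used for both. The Holman Index primary endpoint does not use these formulas, and no between-arm bias is claimed. The additive error and the undefined fluid term are smaller, but they sit in the same derivations. This should be fixed before the tables are programmed.

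**What to change.** 1. Remove the 24/duration factor from SAP 2.4.3.1 and 2.4.3.3. Define daily intake as the total amount ordered or administered that day ÷ dosing weight (weight that day for IV fluids), consistent with 2.5.2.6 and the enteral formulas. State how volume is assigned to days if an infusion record spans more than one.
2. State that the calorie formula uses unscaled volume.
3. If a 24-hour rate is also wanted, report it as a separately labelled variable and say whether duration is planned or actual.
4. In SAP 2.4.3.2, change the additive term in administered lipid from ordered to received.

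The cost is SAP formula edits and reprogramming; no new data are needed.

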5.5 Blinding

The study will be double-blinded. The study treatment assignment will not be known by the Sponsor's or designee's data management, biostatistician (with the exception of an unblinded Sponsor's statistician who will have access to the randomization assignments), and medical functions; Investigator and site personnel; or by the personnel at the central laboratory. In order to prepare the study treatment, the designated pharmacist(s) will be aware of the study treatment (unblinded).

The unblinded pharmacist(s) will prepare the treatment according to the randomization schedule and will enter the required information on the study drug labels. These labels will not contain specific information pertaining to the identity of the study treatment. In addition, specified fields on the label will be blank so that the pharmacist(s) can enter the patient number, as well as other patient identifiers and information as applicable by local procedures. The labels will then be affixed to study treatment containers (either sterile syringes or flexible IV bags, as appropriate for the volume of infusate).

A Data and Safety Monitoring Board (DSMB) will be appointed by Baxter Healthcare Corporation to provide ongoing evaluation of safety data (refer to Section 10.8). Reports will be provided to the DSMB at pre-specified intervals.

Blinded data will be entered into the database and the treatment group assignments will be revealed after database lock.

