6.7.2.4 Fatty acid profiles, Holman Index, and phytosterol, cholesterol, and squalene levels

Blood samples for the determination of FA profiles, Holman Index, and phytosterol (stigmasterol, campesterol, sitosterol), cholesterol, and squalene levels will be collected at Baseline from all patients enrolled in the study. Subsequent samples for FA profiles will be collected on an approximately 15-day basis at least 4 hours after interrupting ILE infusion in order to decrease the influence of infused ILE on FA profile. If a study site typically infuses ILE over 24 hours, the investigator should, to the best of their ability,

ensure a 4-hour lipid only infusion hold before obtaining samples for the FA profiles. Ongoing infusion of other macro- and micronutrients from PN are allowed as required for the best interest of the patient per the attending physician during the 4-hour ILE hold before obtaining samples for the FA profiles. Blood sample volumes will be kept to a minimum.

Blood samples for FA profiles, determining Holman Index, and quantifying the amount of phytosterols, cholesterol, and squalene in samples will be processed by an external laboratory. The FAs will be assessed according to the Mayo Clinic method, which is performed as a 2-step acid-base hydrolysis followed by hexane extraction and derivatization with pentafluorobenzyl bromide. Separation and detection are accomplished by capillary gas chromatography electron-capture negative ion-mass spectrometry. Quantitation is based on analysis in the selected ion-monitoring mode by using 13 stable isotope-labeled internal standards. Handling, labeling, and shipping procedures will be detailed in separate Laboratory Instructions provided by the Sponsor.

Reference values can be found in Appendix 2.

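### Administered PN energy scales lipid calories by a volume ratio that appears to belong to the non-lipid PN solution, so it is wrong whenever lipid and PN solution are delivered in different fractions of their orders

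*SAP*

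**What the plan says.** SAP 2.4.3.1 builds ordered PN energy from three parts: protein at 4 kcal/g, dextrose at 3.4 kcal/g, and lipid as "Lipid intake (g/kg) * lipid dosing weight (kg) * 10". The sum is divided by PN dosing weight and multiplied by 24 over the PN infusion duration. Administered PN energy is then volume administered divided by "Total Volume Ordered* Energy Intake Ordered", so one ratio is applied to the whole sum.

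The SAP does not define that volume. In the same section it is paired with PN dosing weight and PN infusion duration in the fluid formula. In the carbohydrate formula it carries the dextrose ("Dextrose intake (g/dL) * Total volume ordered (mL"). Both uses point to the non-lipid solution.

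Lipid is handled separately. Its administered intake comes from "Total lipid volume administered (mL", with its own infusion duration and its own dosing weight, for which the PN weight is only a fallback: "If lipid dosing weight is missing, PN dosing weight will be used instead". Protocol 5.5 has the study lipid dispensed in its own container, "either sterile syringes or flexible IV bags". Protocol 6.7.2.4 asks sites that infuse lipid over 24 hours to "ensure a 4-hour lipid only infusion hold before obtaining samples for the FA profiles", and lets the rest of the PN run during that hold.

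**The concern.** The SAP works out how much lipid was given but does not use that result when it works out how much energy was given. Lipid calories follow the delivery of a different fluid. On a day when the lipid infusion stops early and the PN solution is completed, the undelivered lipid calories count as delivered. On a day when the PN solution stops early and the lipid is completed, delivered lipid calories are dropped.

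Prescribed against actual intake is part of the nutritional-adequacy secondary endpoint. Administered PN energy feeds overall administered energy and the PN and EN percentages in SAP 2.4.3.4, with their tables and box plots. Lipid is also the randomized product. If lipid interruptions differed between arms, the descriptive comparison of energy would be distorted, and administered lipid and administered energy could disagree for the same patient-day.

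**Working it through.** The SAP gives no worked energy figure to reproduce. As a unit check, Protocol 6.8.5 gives 0.2 g/mL and 2 kcal/mL for both emulsions, so 2 / 0.2 = 10 kcal/g, which matches the SAP factor.

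**Formula.** Let f_PN and f_L be the fractions of the ordered PN solution and ordered lipid that were given. Let N be ordered protein plus dextrose kcal/kg and L ordered lipid kcal/kg. Take 24-hour infusions and equal dosing weights.

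- SAP: f_PN x (N + L)
- By component: f_PN x N + f_L x L
- Error: L x (f_PN - f_L)

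**Assumed order.** Lipid 3, amino acids 3 and glucose 12 g/kg/day. Each lies within the preterm and term-infant macronutrient targets in Protocol Table 3. The total is below that table's energy target of at least 90 kcal/kg, so this is an illustration, not a typical patient.

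- Lipid: 3 x 10 = 30
- Amino acids: 3 x 4 = 12
- Glucose: 12 x 3.4 = 40.8
- N = 52.8, L = 30, ordered energy = 82.8 kcal/kg

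| PN solution given | Lipid given | SAP result | By component | Error |
|---|---|---|---|---|
| 100% | 100% | 82.8 | 82.8 | 0 |
| 100% | 20/24 | 82.8 | 52.8 + 25 = 77.8 | +5.0 (+6.4%) |
| 100% | 50% | 82.8 | 52.8 + 15 = 67.8 | +15.0 (+22%) |
| 100% | 0% | 82.8 | 52.8 | +30.0 (+57%) |
| 80% | 100% | 66.2 | 42.2 + 30 = 72.2 | -6.0 (-8.3%) |
| 80% | 80% | 66.2 | 66.2 | 0 |

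**Lower lipid order.** If the lipid order is cut to 1.5 g/kg and everything is given, ordered energy is 52.8 + 15 = 67.8, the ratio is 1 and administered energy is 67.8. There is no error.

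**If the volume includes lipid.** Assume the 12 g/kg glucose comes as 120 mL/kg of 10% dextrose. Lipid is 3 / 0.2 = 15 mL/kg. With half the lipid given, the ratio is (120 + 7.5) / 135 = 0.944 and the formula gives 78.2 against 67.8, an error of +10.4 kcal/kg (+15%). It is smaller but remains, because lipid carries more energy per mL (2 kcal, against 52.8 / 120 = 0.44 for the rest).

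**Can the existing lipid line be substituted?** Not safely. SAP 2.4.3.1 multiplies administered lipid by 24 over lipid infusion duration. If the recorded duration is the actual one, which the SAP does not say, half of a 3 g/kg dose stopped at 12 hours becomes 24 x 1.5 / 12 = 3.0 g/kg, the full dose again. Likewise 3 g/kg given over 20 hours becomes 24 x 3 / 20 = 3.6. SAP 2.5.2.6 derives an Administered Daily Dose without this factor: volume x 0.2 / lipid dosing weight.

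**The case against.** The strongest reply is that the trigger is narrow and the reach short. Much of this stands.

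- A reader might infer that energy is wrong whenever lipid is reduced. It is not. A reduced order lowers ordered energy too; only delivery that departs from the day's order, in a different proportion from the PN solution, produces an error.
- A reader might infer that energy is always inflated. The error has either sign, and its net direction is unknown.
- A reader might take the 4-hour hold as a built-in overstatement of 6.4%. That holds only if the held lipid is never given. Protocol 5.2 lets the daily dose run over 20 to 24 hours at up to 0.15 g/kg/hour, and 0.15 x 20 = 3.0 g/kg, the Table 4 maximum. A day with a hold can deliver the whole order.
- A reader might infer that the nutritional-adequacy endpoint as a whole is unsound. Fluid, protein, carbohydrate, lipid and growth do not use this energy formula. A lipid shortfall remains visible in the Administered Daily Dose.
- That the volume is the PN solution is an inference. It is well supported by the neighbouring formulas, and the error survives the other reading.

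None of this rescues the formula. It remains incorrect for any patient-day on which the two fluids are delivered in different fractions, and the protocol lets lipid stop while the rest of the PN runs.

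**Conclusion.** The derivation is inconsistent and should be corrected. The error is ordered lipid kcal x (fraction of PN solution given - fraction of lipid given). In the assumed 82.8 kcal/kg order this is +15 kcal/kg (+22%) with half the lipid and all the PN solution given, and -6 kcal/kg (-8.3%) with 80% of the PN solution and all the lipid given.

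The kcal figures rest on an assumed order, equal dosing weights and 24-hour infusions. The documents give neither the frequency of unequal delivery nor any sign that it differs by arm, so neither the effect on group summaries nor a bias between arms can be claimed. The reach is limited to administered PN energy, overall administered energy and the PN and EN energy percentages. These are descriptive, with no hypothesis test planned, and the Holman Index-based EFAD endpoint does not use them.

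**What to change.** In SAP 2.4.3.1, replace the administered-energy formula with:

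administered PN energy (kcal/kg/day) = 4 x protein given + 3.4 x dextrose given + 10 x lipid given

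Each term is g/kg actually given that day, from its own administered volume and without the 24/duration factor:

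- Protein: ordered g/kg x PN volume administered / PN volume ordered.
- Dextrose: g/dL x PN volume administered / 100 / PN dosing weight.
- Lipid: the Administered Daily Dose of SAP 2.5.2.6, not the duration-normalised lipid intake of 2.4.3.1.

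Put ordered energy on the same daily basis, so that ordered and administered can be compared. State in one line that the volume in the fluid and carbohydrate formulas excludes lipid, if that is so. Where lipid and PN dosing weights differ, say which weight divides the total; the ordered formula already converts lipid to kcal with its own weight and divides by the PN weight.

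The cost is a SAP text edit and reprogramming of one derivation and its downstream totals and percentages. The inputs are already used elsewhere in the SAP. The protocol asks for prescribed and actual energy intake but gives no PN energy formula, so no protocol amendment follows from this.
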